# 12.2 Statistic analysis

Descriptive analysis:

Initially, the normal distribution characteristics of all the trial variables will be evaluated, especially that of the main variable BACS.

Comparative analysis between cases vs controls:

A comparison of means will be made by means of T test of dependent samples of the main variable BACS between both arms in the first period. Subsequently, the same analysis will be carried out in the second period, comparing T test of dependent samples means with a 95% confidence margin. If necessary, the Mann-Whitney Test would be applied.

In addition, a study will be carried out where the same sample is compared in period 1 and 2 and a repeated measures analysis will be carried out. That is, the change in the variables of the same patient will be evaluated when he has the experimental drug compared to when he is with his usual treatment. In the same way, it will be done with the mean of the sample of each arm and period.

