# 6.3 Randomization procedure

Patients will be recruited within the health area corresponding to the center participating in the trial, the Virgen del Rocío University Hospital in Seville. They will be detected from institutionalized patients who attend the mental health network devices on an outpatient basis.

In those patients with a diagnosis of early evolution Schizophrenia with a stable treatment with antipsychotics for at least 4 weeks, the inclusion and exclusion criteria of the study will be verified, and informed consent will be requested after completing the ACE questionnaire, to measure the degree capacity of understanding of the person who signs. Patients who meet all the inclusion criteria, but have some exclusion, will be considered screening failure, and the reason for exclusion should be collected. Subjects who drop out of the trial before the end of the trial will not be replaced.

Once the informed consent has been signed, randomization will be carried out, which will be centralized online, in a 1: 1 ratio (adjuvant treatment with vortioxetine vs treatment in usual clinical practice).

The randomization system will be available online in the CRDe (Electronic Data Collection Notebook) designed for this purpose. The list of assignments will be generated using specific software and will be included in the CRD.

The randomization list will be guarded by the Clinical Trials Unit (UICEC). Once you have entered that you meet all the inclusion criteria and none of the exclusion criteria, the researcher will obtain the assigned treatment and the patient's code, which will be made up of a numerical code that identifies the center and patient (per example: XX-XXX).

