# 9.1 Procedures per visit

The follow-up of the patients in the present study consists of 9 scheduled visits in each period (18 in total). Depending on which arm the patient falls on, the trial treatment will begin in one period or another. That is, if after the randomization of the patient, he falls into the Experimental Arm, the treatment will begin on Visit 2 (Day 1) and will end in week 24, corresponding to period 2 as the TAU treatment period. If, on the other hand, the patient falls into Control Arm, the study will begin with a first TAU period (continues with the treatment according to clinical criteria) and it will be in period 2 when the trial treatment begins (in week 26 of the study).

In this protocol the visits are arranged in chronological order, specifying the week to which each one corresponds.

The following sections detail the procedures that must be carried out at each visit.

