#### 12.- STATISTICS

# 12.1 Sample size calculation

As it is a crossover design, each individual acts as their own control, that is, an initial treatment is assigned and after a while it is changed. Therefore, the correct thing to do would be to calculate the sample under the premise of related or paired samples, for this case it would be the dependent samples T test.

The sample size can be calculated in two ways, in the first one, the difference in the means to be detected of the primary variable (BACS), the standard deviations of the treatment change, and the correlation coefficient must be established; while the second is to consider the difference in the means to be detected for the primary variable (BACS) and the standard difference of the differences.

Accepting an alpha risk of 0.05 and a beta risk of 0.2 in a bilateral contrast, 37 subjects are required to detect a difference equal to or greater than 0.5 units. A standard deviation of 1 is assumed. A loss to follow-up rate of 15% has been estimated.

That is, based on the previous parameters, and using a confidence level of 95% and power of 80%, 37 subjects are needed.

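### Section 12.2 prescribes a paired t test between two arms made up of different patients, gives it an independent-samples fallback, and does not name the within-patient contrast sized in 12.1 as primary

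*Protocol*

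**What the plan says.** Section 12.2 gives three comparisons of the main variable, in this order:

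- In period 1, a "T test of dependent samples of the main variable BACS between both arms in the first period".
- In period 2, the same test: "Subsequently, the same analysis will be carried out in the second period". For these comparisons the fallback is: "If necessary, the Mann-Whitney Test would be applied".
- Then the within-patient comparison: "In addition, a study will be carried out where the same sample is compared in period 1 and 2". It is described as a repeated measures analysis of each patient's change on the experimental drug against the change on usual treatment.

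No section says which of the three decides the primary endpoint.

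Two other sections fix the data structure. Section 6.3 randomises "in a 1: 1 ratio (adjuvant treatment with vortioxetine vs treatment in usual clinical practice". Section 9.1 explains that a patient allocated to the experimental arm starts vortioxetine at Visit 2 and has usual treatment in period 2, while a patient allocated to control does the reverse.

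Section 12.1 sizes the trial on each patient as his or her own control. It says of the test that "for this case it would be the dependent samples T test", and concludes that "37 subjects are required to detect a difference equal to or greater than 0.5 units".

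**The concern.** A dependent-samples t test needs a natural pair for every observation. In this crossover the pair is one patient's two periods. Within a single period the two arms hold different randomised patients, and the protocol describes no matching. The test named first in 12.2 therefore does not fit the comparison it is attached to. The fallback assumes the opposite data structure, so parametric test and fallback cannot both be right for the same comparison.

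The within-patient contrast, which does suit a paired test and on which the sample size rests, comes last and has no stated status. If 12.2 is followed in the order written, the leading efficacy result comes from a test that cannot be run or depends on how rows are matched. Corrected to an independent test, it is a comparison for which 37 patients give much less than 80% power. The trial is open-label, and with no primary test named the conclusion could be drawn from whichever of the three analyses is preferred once results are known.

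**Working it through.** **Inputs.** From 12.1: two-sided alpha 0.05, power 80%, difference 0.5, SD 1, loss 15%, total 37. From 6.3: allocation 1:1, so 19 v 18, and about 16 v 15 after 15% loss (37 × 0.85 = 31.45, taken as 31). The protocol gives no correlation r between a patient's two period changes; 0, 0.3, 0.5 and 0.7 are assumed.

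**1. The protocol's own figure.** Section 12.1 does not say what the SD of 1 refers to. Read as the SD of within-patient differences:

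n = (1.960 + 0.842)² × 1² / 0.5² = 31.4; 31.4 / 0.85 = 36.9, so 37.

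The figure is reproduced. The same normal formula for two independent groups at SD 1 needs 63 per arm, so 37 is not a two-group figure.

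**2. Power of the within-patient contrast.** With 31 completers the noncentrality is 0.5 × √31 = 2.78 on 30 df, giving 76.8%. With a period term and 16/15 completers per sequence it is 0.5 / [0.5 × √(1/16 + 1/15)] = 2.78 on 29 df, giving 76.7%.

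**3. Power of a valid independent test in one period.** If the SD of the within-patient differences is 1, the SD of a single period change is 1/√(2(1 − r)). Noncentral t, difference 0.5:

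| assumed r | SD of a period change | power, 19 v 18 | power, 16 v 15 | evaluable per arm (total) for 80% |
|---|---|---|---|---|
| 0 | 0.707 | 55% | 48% | 33 (66) |
| 0.3 | 0.845 | 42% | 36% | 46 (92) |
| 0.5 | 1.000 | 32% | 27% | 64 (128) |
| 0.7 | 1.291 | 21% | 18% | 106 (212) |

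At r = 0.5 the exact calculation gives 64 per arm, against 63 from the normal formula in step 1.

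**4. What arbitrary pairing does.** Take 18 v 18 and an observed difference of exactly 0.5 pooled SD. The independent test gives t = 0.5/√(2/18) = 1.5 on 34 df, p = 0.14. Over 200 simulated normal data sets with 2,000 random pairings each, the paired p ran on average from 0.06 to 0.23 over the central 95% of pairings. The average smallest and largest values were about 0.015 and 0.27. The same data can fall on either side of 0.05 depending on the pairing.

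**5. Any of three.** If a positive result on any one of the three tests counted, the simulated type I error is about 12% for every r above (40,000 runs, 16/15). The protocol states no such rule, so this only shows what is at stake in leaving the primary test unnamed.

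**The case against.** The best defence is that the intended contrast is in the protocol. The synopsis calls each patient an own control, 12.1 sizes on the paired test, and the last paragraph of 12.2 describes the same patient on and off the drug. On this view the word for dependent samples is a slip (the Mann-Whitney fallback suggests an independent test was meant), and the formal primary label can wait for a statistical analysis plan. This makes the cure easy. It does not make the text right: the protocol names a specific test for a specific comparison, repeats it for the second period, and the two do not fit. A plan that put this right would contradict the protocol.

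Secondly, pairing fixed without sight of outcomes, such as by enrolment order, keeps the 5% level (4.9% in 200,000 simulated null data sets, 18 v 18) and loses little power. That is correct, so the paired test need not inflate error. The result would still depend on a pairing that the protocol does not define, and with 19 v 18 a patient is left over.

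Thirdly, low power in a supportive comparison is no error. True, but 12.2 does not call the within-period comparisons supportive. The synopsis also mentions 25 per arm and 50 patients. With 25 v 25 the one-period power is 69%, 54%, 41% and 27% for the four correlations, still below 80%.

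**Conclusion.** The point holds and must be fixed. The within-period test is wrong as written, its fallback assumes a different data structure, and the analysis that justifies 37 patients is not identified as the one that decides the trial. None of this depends on an assumption.

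The size does depend on assumptions: that the SD of 1 is that of the within-patient differences (the reading that reproduces 37) and that r lies between 0 and 0.7. On that basis the sized contrast has about 77% power with 31 completers, against 18% to 48% for a correct single-period test after the planned loss and 21% to 55% before it.

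**What to change.** In 12.2, state one primary test at two-sided 5%: the within-patient difference, vortioxetine minus usual treatment, in period change of the BACS App composite. Analyse it with a period term, by the period-adjusted two-sequence t test or an equivalent mixed model, and give as fallback a rank test on the within-patient period differences. Keep the period-1 comparison between arms as supportive only, with an independent-samples t test, or Mann-Whitney if the data are clearly non-normal.

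The period term is a precaution. A repeated measures analysis does not exclude it, and sections 9 and 10.1 mention alternate test versions that limit practice or recall effects. If a period effect remained (assumed 0.3 to 0.5) and were left out, power would fall. The estimate would also be biased by the period effect × (n1 − n2)/(n1 + n2), where n1 and n2 are the completers in the two sequences: 0.01 to 0.02 at 16/15, 0.03 to 0.05 at 17/14 and 0.05 to 0.08 at 18/13.

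The cost is wording. No new patients or data are needed, and the period term takes one degree of freedom (76.7% power against 76.8% with 31 completers).

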#### 4.- JUSTIFICATION

Comprehensive meta-analysis reviews consistently show marked impairments in a wide range of cognitive domains in schizophrenia, with considerable long-term effects. The effects tend to be somewhat higher especially for tests that assess memory and processing speed. The patients are cognitively outperformed by the controls at the onset of the disease, and the cognitive performance of the patients improves in a similar way to the controls over time (Rodriguez-Sanchez et al, 2013). Although the course of cognitive performance is generally stable, there is a subset of patients who experience cognitive decline over time. Patients whose cognitive performance experiences a decreasing trend show poorer progression in terms of clinical and disability variables.

The degree of baseline impairment in cognitive functions related to the prefrontal cortex are critical determinants of quality of life and functionality in schizophrenia (Treen Calvo et al. 2018 FEP). Therefore, cognition is an important goal of treatment, given the strong association between it and functional outcomes in people with psychotic disorders. Antipsychotics are quite effective in reducing the severity of positive symptoms and preventing relapse, but their impact on negative and cognitive symptoms is limited. In the last two decades, different strategies have been proposed to treat cognitive impairment in schizophrenia with uncertain achievements (Robbins et al, 2019). Cognitive enhancement agents are pharmaceuticals that are suggested to enhance cognitive performance by acting on the relevant neurotransmission systems, typically the glutamatergic and cholinergic systems. Results from individual studies have been mixed, and a recent metaanalysis of 93 studies, comparing cognitive enhancement agents with placebo, reported a small significant effect of cognitive enhancers on general cognition, but no significant effects on cognitive domains, individual. The main limitations are that many of these studies are underpowered to detect effects, that the number of studies investigating these agents is few, and the treatment durations are short (Sinkeviciute et al, 2018; Keefe et al, 2013).

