# 6.6 Discontinuation of study treatment and withdrawal of subjects from the study

Premature discontinuation of the clinical trial may occur due to a decision of the regulatory authorities, due to a change in the opinion of the Clinical Research Ethics Committees, due to safety and / or drug problems or indications of ineffectiveness.

It will be considered that there is a voluntary abandonment of the trial due to the refusal of the patient or legal guardian of the same to continue with the treatment or in the study, and the subject will be considered as abandonment immediately after communicating his decision to the Investigator. A patient may discontinue the trial at any time if the person, the legal representative, the investigator or the motorization committee determine that it is not in the best interest of the patient to maintain their participation.

Other reasons for discontinuation include:

- Patients with low compliance with the study drug, below 80%
- Patients requiring hospitalization for worsening psychotic disorder and / or behavioural disturbances associated with psychotic disorder.
- Patients in whom, during the study period, there is a high risk of detected suicide, according to the criteria established by Columbia University according to the risk assessment with the C-SSRS scale.
- Female patients who test positive for urine pregnancy at any time during their participation in the study.
- Any serious adverse event that recommends withdrawal at the discretion of the investigator with the agreement of the monitoring committee.
- The patient decides not to continue with the trial.
- Others: The researcher, as well as the sponsor, reserve the right to interrupt the study at any time for reasonable medical and / or administrative reasons.

Patients who drop out after randomization will not be replaced.

Patients who terminate treatment prematurely will complete an early termination interview and a safety visit.

The patient who has completed the protocol is considered to be one who has completed all the visits included in the 52-week follow-up period.

The interruption of the treatment does not imply that the case is excluded from the statistical analysis. These subjects will be part of the study and will be taken into account when analyzing the data.

There may be other circumstances for the abandonment, which in its case the researcher must make sure that the patient has abandoned the study, and will verify the causes of said abandonment.

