#### CAVES PROTOCOL CONFIDENTIAL VERSION 1.0

Hematology/Chemistry 		Х							Х
Dispense Treatment 11		Х	Х	Х	Х	Х	Х	Х	
Compliance 12			Х	Х	Х	Х	Х	Х	Х
Concomitant Medication	X	Х	Х	Х	Х	Х	Х	Х	Х
Adverse Events			Х	Х	Х	Х	Х	Х	Х

- 1. Between week 24 and week 26 the first wash period takes place. The washing time between one period and another will be 2 weeks
- 2. HAMD-17: Hamilton Rating Scale for Depression
- 3. BARS: Behaviorally Anchored Rating Scale
- 4. PANSS: Positive and Negative Syndrome Scale
- 5. SAS: Sedation-Agitation Scale
- 6. SANS: Scale for Assessment of Negative Symptoms
- 7. BACS: Brief Assessment of Cognition in Schizophrenia
- 8. BACS App: Brief Assessment of Cognition in Schizophrenia App. Versión de la Escala BACS en aplicación para Tablets: facilitará la realización de pruebas repetidas y reducirá efectos de la práctica. Existen diferentes versiones de la prueba.
- 9. NSA-4: Negative Symptom Assessment (4-Item)
- 10. GAF: Global Functionality Assessment Scale
- 11. Vortioxetine dosage according to Summary of Product Characteristics (section 6.5 of protocol)
- 12. Patient must bring test medication at each visit for counting. Empty boxes will stay in the center
- 13. Complete blood count including leukocyte, neutrophil, hemoglobin, and platelet counts. Blood chemistry that includes the determination of sodium, potassium, creatinine, urea, lipid profile, glycemia.

CAVES PROTOCOL CONFIDENTIAL VERSION 1.0

Procedures PERIOD 2	Visit10 (Day 183±3) Week 26	Visit11 (Day 190±3) Week 27	Visit12 (Day 211±3) Week 30	Visit13 (Day 239±3) Week 34	Visit14 (Day 267±3) Week 38	Visit15 (Day 295±3) Week 42	Visit16 (Day 323±3) Week 46	Visit17 (Day 351±3) Week 50 	Visit18 (Day 379±3) Week 52
Pregnancy Test	Х								X
Medical History	Х	Х	Х	X	Х	Х	Х	Х	X
HAMD-17	Х								
BARS	Х								
PANSS	Х							Х	Х
SAS	Х	Х	X	X	Х	Х	Х	Х	
SANS	X		X		Х			Х	
BACS	X				Х			X	Х
BACS App	X							X	
NSA-4	X		X		Х			X	
GAF	X				Х			X	Х
Vitals Signs: weigth, Height, Blood Pressure, Pulse Rate, abdominal perimeter	х		х		Х			х	Х
Hematology/Chemistry	X							X	Х
Dispense Treatment	X	Х	X	Х	Х	X	X		
Compliance		Х	X	Х	Х	Х	X	X	
Concomitant Medication	X	Х	X	Х	Х	X	X	X	Х
Adverse Events	X	X	X	X	Х	X	X	X	X

1. Between week 50 and week 52 the second wash period takes place. The visit corresponding to week 52 corresponds to the FINAL VISIT OF THE TRIAL.

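### The within-patient comparison in 12.2 has no stated period term, so any difference in mean change between the two periods would cost power and, with unequal sequences, shift the estimate

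*Protocol*

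**What the plan says.** Section 12.1 treats the crossover as paired data and concludes that "for this case it would be the dependent samples T test". Its figures are "Accepting an alpha risk of 0.05 and a beta risk of 0.2 in a bilateral contrast", with the result that "37 subjects are required to detect a difference equal to or greater than 0.5 units"; "A standard deviation of 1 is assumed", and 15% loss is allowed for.

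Section 12.2 first compares the arms within period 1 and then within period 2. It adds a repeated measures analysis and explains it as a contrast within the patient: "the change in the variables of the same patient will be evaluated when he has the experimental drug compared to when he is with" usual treatment. It closes by mentioning means for each arm and period. No period or sequence factor is named, and the two within-period comparisons are not combined into one estimate.

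Other relevant text:
- Section 6.1.1 gives each period its own baseline: baseline to week 24, then week 26 to week 50.
- The notes to the section 9 schedule say, in Spanish, that the App "facilitará la realización de pruebas repetidas y reducirá efectos de la práctica", meaning that it will make repeated testing easier and reduce practice effects.
- Section 6.3 allocates 1:1 and states no blocking. Section 6.6 does not replace dropouts, and says of patients who stop treatment: "These subjects will be part of the study and will be taken into account when analyzing the data".

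**The concern.** In a two-period crossover, each patient's difference between treatments is also a difference between periods. If the mean change on the same treatment is not equal in the two periods, a plain paired comparison mixes that inequality with the treatment effect.

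The protocol gives a concrete reason to expect some inequality. By the section 9 schedule, the period-1 change starts at the first BACS and BACS App session. By week 26 the patient has taken the App twice (baseline and week 24) and the paper BACS three times (baseline, weeks 12 and 24), the last time two weeks earlier. Section 9.1.9 omits the App at week 24, so the App count may be one, but the exposure still differs. If the gain from practice is largest at the first retest and then levels off, the period-1 change will be larger.

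At stake are power and the accuracy of the main crossover estimate. A paired comparison also cannot use a patient who has only one period.

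**Working it through.** **Inputs.** From 12.1: two-sided alpha 0.05, power 80%, difference 0.5, SD 1, loss 15%. The text does not say which SD it means. It is read here as the SD of the within-patient difference; SD 1 per period with correlation 0.5 gives the same value. The period effect π is not in the protocol and is assumed to be 0.2 to 0.5. The upper end equals the whole target effect.

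**The plan's own figure.** n = ((1.960 + 0.842) × 1/0.5)² = 31.40, and 31.40/0.85 = 36.94, so 37. It reproduces. Completers: 37 × 0.85 = 31.45, so about 31. Exact paired-t power at 31 pairs is 76.8%.

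**Algebra.** Let π be the mean period-1 change minus the mean period-2 change on the same treatment, τ the treatment effect, and D the change on vortioxetine minus the change on TAU.
- Vortioxetine first (n1 patients): E(D) = τ + π.
- TAU first (n2 patients): E(D) = τ − π.
- Plain mean of D: τ + π(n1 − n2)/n.
- Variance seen by the paired test with equal sequences: about SD² + π².
- Unweighted mean of the two sequence means: τ, whatever π is.

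Bias at 13/18: −5/31 × 0.2 = −0.03 and −5/31 × 0.5 = −0.08. At 20/11: 9/31 × 0.2 = +0.06 and 9/31 × 0.5 = +0.15. At 16/15: 1/31 × 0.5 = +0.02.

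**Simulation** (D normal, SD 1, 31 completers, true effect 0.5; type I error at effect 0; splits are vortioxetine-first/TAU-first):

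| Split | π | Bias, paired | Power, paired | Power, adjusted | Type I error, paired |
|---|---|---|---|---|---|
| 16/15 | 0.2 | +0.01 | 77% | 77% | 4.6% |
| 16/15 | 0.5 | +0.02 | 72% | 77% | 2.9% |
| 18/13 | 0.2 | +0.03 | 81% | 76% | 4.9% |
| 18/13 | 0.5 | +0.08 | 82% | 76% | 4.4% |
| 13/18 | 0.2 | −0.03 | 70% | 76% | 4.9% |
| 13/18 | 0.5 | −0.08 | 53% | 76% | 4.5% |
| 20/11 | 0.2 | +0.06 | 84% | 73% | 5.7% |
| 20/11 | 0.5 | +0.15 | 90% | 73% | 8.4% |

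The higher paired power at 18/13 and 20/11 comes from the upward bias and is not a gain. The adjusted analysis is unbiased with about 5% type I error in every row.

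**How likely is imbalance?** If allocation were simple, a completer gap of 5 or more among 31 has probability 0.47, and a gap of 9 or more has probability 0.15. Blocking would lower both. Averaged over simple randomisation, the paired test has no bias and about 5% type I error at every π from 0.2 to 0.5. Its power is about 75% at π = 0.2 and 67% at π = 0.5.

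**The case against.** The best reply is that the model is unspecified rather than wrong. Section 12.2 promises a repeated measures analysis without listing factors, a t test used for sizing does not rule out a period term, and model terms are often left to a statistical analysis plan. This stands in part: a period factor is not excluded. But 12.2 does say what the analysis is, the contrast it describes has no period in it, and 12.1 calls the paired t test the appropriate one. The means by arm and period describe the data and adjust nothing.

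Second, comparisons within one period contain no period effect, and averaging them would give the adjusted estimate. That is true, but the plan does not combine them. It does mean that the plan as a whole uses patients with period 1 only. Only the paired comparison leaves them out, so a reader who infers that the plan discards them against section 6.6 goes too far.

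Third, a reader might infer that expected cognitive drift biases the endpoint. The documents do not support this. Section 4 does report from the literature that "the cognitive performance of the patients improves in a similar way to the controls over time", but the next sentence calls the course generally stable. Steady drift also adds the same amount to two 24-week changes with separate baselines, and so cancels. Only a gain that differs between periods matters.

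Fourth, the protocol does not say that the App is practice-sensitive. It says that practice effects will be reduced and that different versions of the test exist. A remaining effect is plausible, but its size is unknown and it may be small.

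**Conclusion.** The point holds in a limited form. No period or sequence term is stated for the within-patient comparison, and the two baselines differ in test exposure, so a period difference in the primary change score is plausible.

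The size rests on an assumed π of 0.2 to 0.5 and on SD 1 for the patient difference. Near balance the harm is lost power only: under 1 point at π = 0.2 and about 5 points at π = 0.5. At 13/18 the estimate is 0.03 to 0.08 too low and power falls to between 70% and 53%. Type I error exceeds 5% only under marked imbalance, at about 6% to 8% for 20/11.

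A reader might infer that the trial's estimate is biased or its error rate inflated in general. That is not supported. Both depend on the realised split and average out under simple randomisation unless dropout differs by sequence, for which the protocol gives no figure. This is a recommended, cheap improvement and not a must-fix.

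**What to change.** In 12.2, state that the within-patient analysis is a crossover analysis with period. Either form will do:
- Compute each patient's change on vortioxetine minus change on TAU, average it within each sequence, and take the unweighted mean of the two sequence means as the treatment effect, with n − 2 degrees of freedom.
- Fit a mixed model to the period changes with treatment, period and patient, using every available change, including those of patients with one period.

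Report the period estimate with its confidence interval. Settle this before data are seen, because in an open-label trial a period term chosen later could look data-driven.

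The cost is wording only, with no extra patients or visits. If there is no period effect, the adjustment loses about 0.2 power points near balance, 1 at 18/13 and 4 at 20/11. In return, the mixed model can use patients with period 1 only: 2 to 6 of them add about 1.5% to 10% information, assuming a between-period correlation of changes from 0.5 down to 0.
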